6.6 Post Procedures and Outcomes

Follow-up visits are scheduled for appointed times after the date of the procedure. It is important that this schedule is adhered to as closely as possible for all subjects. Study visits not completed within these time periods will be regarded as deviations. A study visit should be scheduled as closely as possible to the earlier part of the time period to allow for possible re-scheduling, thereby preventing a deviation. All subjects will be asked to return to the clinic at intervals described in **Table 1**. Device programming and radiographic lead positioning confirmation visits are anticipated unscheduled visits and do not represent protocol deviations, and may occur *ad hoc*.

The following post-operative data will be collected:

- NRS for the index site pain
- ODI
- EQ-5D
- Global Improvement Impression of Change (PGIC)
- SF-36
- Pain medication usage (dosage and frequency)
- Neurological assessment
- Patient Satisfaction
- Additional intervention(s)
- Complications / Adverse events

Table 1: Schedule of Assessments

Assessment									
	Pre-op	Trial Procedure	Trial Removal Follow-up 7 (+/- 3 days)	Implant Procedure	Post-Operative Follow-up 10 (+/- 3 days)	Follow-up Visit (30 days +/- 7 days)	Follow-up Visit (3 months +/- 14 days)	Follow-up Visit (6 months +/- 14 days)	Unscheduled Visit
Informed Consent	X								
Medical & Interval History	X	X	X	X	X	X	X	X	X
Demographics	X								
Physical Exam / Neurological Assessment	X	X	X	X	X	X	X	X	X
Pain Scales (NRS) & Pain Medication Usage	X	X	X	X	X	X	X	X	X
Oswestry Disability Index (ODI)	X					X	X	X	
EQ-5D	X					X	X	X	
Global Improvement Impression of Change (PGIC)			X		X	X	X	X	
SF-36						X	X	X	
Patient Satisfaction	X		X		X	X	X	X	
Adverse Events*	X	X	X	X	X	X	X	X	X
Other Interventions		X	X	X	X	X	X	X	X

*Adverse events should be recorded at any time during the course of the study

6.7 Patient Early Discontinuation / Withdrawal and Replacement of Patients

All subjects are informed of their right to withdraw from the clinical study at any time. Additionally, the investigator may prematurely discontinue any patient's participation in the study if the investigator feels that the patient can no longer fully comply with the requirements of the study or if any of the study procedures are deemed potentially harmful to the patient. However, it is anticipated that such withdrawals will be infrequent to ensure the integrity of the study. The reason for early discontinuation will be documented in the source documents and case report forms.

6.8 Lost to Follow-up Patients

Every attempt will be made to have all subjects complete the follow-up visit schedule. A subject will not be considered lost to follow-up unless efforts to obtain compliance are unsuccessful. At a minimum, the effort to obtain follow-up information will include three attempts to make contact via telephone and if unsuccessful, then a certified letter from the investigator will be sent to the subject's last known address. In general, the study site coordinator should attempt to contact the subject after each missed visit to re-schedule the visit or collect patient-reported outcomes via phone interview.

7 Risk / Benefit Analysis

7.1 Benefits

Possible benefits of neuromodulation with either device may include the reduction of pain.

7.2 Risks

Possible risks associated with neuromodulation in either arm include:

- Failure to relieve pain
- Unable to place the device due to anatomical abnormality
- Infection
- Dural tear / CSF leak
- Nerve root irritation or nerve root injury with or without neurological deficit
- Seroma / Hematoma
- Vascular injury
- Bowel / bladder incontinence
- Bleeding
- Epidural fibrosis

Mean radiation exposure with spinal cord stimulation has been estimated at 13.9mGy, range: 1.8mGy-43.7mGy (Wininger, Deshpande and Deshpande 2010).

8 STATISTICAL SECTION

8.1 Statistical Considerations

A binary responder rate for spinal cord stimulation is defined as those subjects who achieved $\geq 50\%$ diminution in pain intensity. Historical responder rates with legacy spinal cord stimulation arrays were nearly 50% (North, et al. 2005). Contemporary responder rates utilizing novel programming algorithms and targeted placement now exceed 80% (Kapural, et al. 2015) (Deer, Levy and Kramer 2017) (Russo, et al. 2018).

8.2 Statistical Software

All statistical analysis will be performed using R Statistical Software Version 3.4.1.

8.3 Determination of the Sample Size

Sample size was determined based on the planned noninferiority test for effectiveness to primary end point of treatment success and contemporary responder rates. Treatment success was defined as $\geq 50\%$ reduction in the Numerical Rating Scale (NRS) score in the index area of pain. Previous data indicated that the success rate of DRG, defined as a 50% reduction in pain intensity, was 81%, and 56% for SCS (Deer, Levy and Kramer 2017). Assuming 15% attrition, an estimated 62 subjects (31 subjects in each arm) would provide greater than 70% power to test the primary end point hypothesis with a noninferiority margin of 5% at the 95% confidence interval.

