8.4 Analysis of the Primary Endpoint

Descriptive statistics for all continuous variables will be presented as number of subjects, mean with SD and median with range and for the categorical variables, number and percentage of subjects will be used. DRG stimulation and SCS will be compared using a 2-sample t test (or Wilcoxon rank-sum test) for continuous outcomes and Pearson χ^2 test (or Fisher exact test) for categorical outcomes. Choice of parametric or alternative tests will be determined based on the data distributions for each measure. Two-sided confidence intervals will be also provided for certain outcome measures of interest to assess differences between the two different treatment arms. The primary end point analyzes the success rate between the two treatment arms using Blackwelder method for testing noninferiority between 2 proportions at a one-sided significance of 0.05 with setting the noninferiority margin at 5 %.

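### Do the 95% confidence interval in the sample-size section and the one-sided 0.05 test in the analysis section set two different rules for the primary endpoint?

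*Combined protocol and SAP*

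**What the plan says.** Section 8.3 takes its planning rates from an earlier trial: "success rate of DRG, defined as a 50% reduction in pain intensity, was 81%, and 56% for SCS". With 15% attrition it arrives at "an estimated 62 subjects (31 subjects in each arm"), and says this number "would provide greater than 70% power to test the primary end point hypothesis with a noninferiority margin of 5% at the 95% confidence interval". It does not say whether that interval is one- or two-sided. The section opens by basing the sample size on the noninferiority test planned for treatment success.

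Section 8.4 defines that test: "Blackwelder method for testing noninferiority between 2 proportions at a one-sided significance of 0.05", with the same 5% margin. The sentence before it says "Two-sided confidence intervals will be also provided for certain outcome measures of interest". It gives no confidence level and does not tie these intervals to the noninferiority decision.

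**The concern.** Many readers take an unqualified 95% confidence interval to be two-sided. Judging noninferiority by the lower limit of such an interval is a test at one-sided 0.025. A test at one-sided 0.05 corresponds to the lower limit of a two-sided 90% interval. Read this way, adjacent sections would give the primary endpoint two error rates, 2.5% and 5%, and the only intervals that 8.4 mentions are indeed two-sided.

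Two things would then be at stake. The stated power might belong to a different rule from the one used in the analysis. A result near the boundary could also pass one rule and fail the other. Patients and staff are not masked (section 6.3), so the primary criterion should not be open to choice once data are in hand.

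**Working it through.** **Inputs** (sections 8.3 and 8.4): success rates 0.81 (DRG) and 0.56 (SCS); margin 0.05; 31 per arm; attrition 15%. Evaluable per arm: 31 × 0.85 = 26.35, so 26 or 27 whole patients.

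**Formula** (normal approximation, unpooled variance): power = Φ[(0.81 − 0.56 + 0.05)/SE − z], where SE = √[(0.81×0.19 + 0.56×0.44)/n] = √(0.4003/n).

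**The plan's figure, under the test in 8.4** (z = 1.645), with n = 26:
- SE = √(0.4003/26) = 0.1241, and 0.30/0.1241 = 2.418.
- Power = Φ(2.418 − 1.645) = Φ(0.773) = 78.0%.

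The claim of more than 70% is reproduced after attrition.

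**The stricter reading** (z = 1.960), with n = 26: Φ(2.418 − 1.960) = Φ(0.458) = 67.7%.

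| Evaluable per arm | One-sided 0.05 | One-sided 0.025 (two-sided 95% interval) |
|---|---|---|
| 26 | 78.0% | 67.7% |
| 26.35 | 78.5% | 68.2% |
| 27 | 79.4% | 69.3% |
| 31 (no attrition) | 84.0% | 75.2% |

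**Other formulas:**

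| Method | One-sided 0.05, n = 26 | One-sided 0.05, n = 27 | One-sided 0.025, n = 26 | One-sided 0.025, n = 27 |
|---|---|---|---|---|
| Exact enumeration of the same test | 77.3% | 78.5% | 68.4% | 69.9% |
| Restricted-likelihood score test (exact) | 77.3% | 78.5% | 65.7% | 67.5% |
| Pooled variance | 76.1% | 77.5% | 64.9% | 66.6% |
| Continuity correction | 67.8% | 69.7% | 55.9% | 57.9% |

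The plan does not call for a continuity correction. That is the only method tried that takes the one-sided 0.05 rule below 70%.

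**Patients needed for 70% power** (normal quantile 0.524), n = (z + 0.524)² × 0.4003/0.30²:
- One-sided 0.05: 20.9, so 21 evaluable; 21/0.85 = 24.7, so 25 per arm.
- One-sided 0.025: 27.5, so 28 evaluable; 28/0.85 = 32.9, so 33 per arm, 66 in total against 62 planned.

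**Can the two rules disagree?** Take DRG 19/26 and SCS 14/26. The difference is 0.1923 and SE = √[(0.7308×0.2692 + 0.5385×0.4615)/26] = 0.1309.
- Lower limit, two-sided 90%: 0.1923 − 1.645×0.1309 = −0.023, inside the margin.
- Lower limit, two-sided 95%: 0.1923 − 1.960×0.1309 = −0.064, outside the margin.

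Under the planning rates, the exact chance of passing only the looser rule is 77.3% − 68.4% = about 9% with 26 per arm.

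**Which rule does the plan set?** Section 8.3 points to the planned noninferiority test. Only 8.4 describes such a test, and it gives the method, the sidedness, the level and the margin. Reading "at the 95% confidence interval" as a one-sided 95% bound makes the sections identical. The figure 0.025 appears nowhere, and no sentence says that noninferiority is judged from a two-sided interval.

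**The case for a change.** The strongest case for a change is that the reconciling reading is not written down. The usual meaning of a 95% interval is two-sided, and on that meaning the stated power is missed at 26 and 27 evaluable per arm by every formula tried. It is reached only when attrition is ignored (75.2% at 31 per arm), although the same sentence assumes attrition. A bound of more than 70% is also too loose to show which level was used, since 78% and 75% both satisfy it. With open-label treatment and about a 9% chance of a result between the two rules, the sidedness could be settled in one phrase.

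The arithmetic stands, and so does the remark that 8.3 is loosely worded. The inference that the plan holds two decision rules does not. The two-sided intervals in 8.4 are additional output for selected measures, and the sentence that follows gives the primary endpoint its own test. Any result near a boundary passes at 0.05 and fails at 0.025; that shows that the rules differ, not that the plan adopts both. An analyst following 8.4 has nothing to choose after seeing the data.

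**Conclusion.** No change follows. The primary test is fully specified in 8.4, and under it the power claim in 8.3 is correct: 78.0% with 26 evaluable per arm, 77.3% by exact calculation. This rests on the plan's own rates of 81% and 56%, its 15% attrition, and no continuity correction.

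If a two-sided 95% interval had been intended, power would fall short of 70% by about 0.1 to 2.4 points with 26 or 27 per arm (unpooled formula and exact enumeration), or by up to 5.1 points with a pooled variance (70 − 64.9). Nothing in the documents establishes that intention.

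Writing the sidedness into 8.3 would make the text clearer but would alter no analysis, sample size or conclusion. Moving the test to one-sided 0.025 would correct no error: it would trade about 10 points of power (78.0% − 67.7%) for a lower false-positive rate. That is a design choice, and the sponsor made it openly in 8.4.

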8.4 Analysis of the Primary Endpoint

Descriptive statistics for all continuous variables will be presented as number of subjects, mean with SD and median with range and for the categorical variables, number and percentage of subjects will be used. DRG stimulation and SCS will be compared using a 2-sample t test (or Wilcoxon rank-sum test) for continuous outcomes and Pearson χ^2 test (or Fisher exact test) for categorical outcomes. Choice of parametric or alternative tests will be determined based on the data distributions for each measure. Two-sided confidence intervals will be also provided for certain outcome measures of interest to assess differences between the two different treatment arms. The primary end point analyzes the success rate between the two treatment arms using Blackwelder method for testing noninferiority between 2 proportions at a one-sided significance of 0.05 with setting the noninferiority margin at 5 %.

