Single Center, Randomized Prospective Comparative Effectiveness Study of Dorsal Column Spinal Cord Stimulation to Dorsal Root Ganglion Stimulation in the Treatment of Complex Regional Pain Syndrome

Version: 1.5

September 19, 2018

Department of Evidence Based Pain Research
Cleveland Clinic
[name]

Protocol Synopsis

Title:	Single Center, Randomized Prospective Comparative Effectiveness Study of Dorsal Column Spinal Cord Stimulation to Dorsal Root Ganglion Stimulation in the Treatment of Complex Regional Pain Syndrome of the Lower Extremity
Investigational Products	
 1. Nuvectra Algovita Dorsal Column Spinal Cord Stimulation System 2. Abbot Proclaim Dorsal Root Ganglion Spinal Cord Stimulation System
Regulatory Status	Post-market evaluation. The indications for both dorsal column and dorsal root ganglion neurostimulation utilized in this study are cleared by the FDA.
Study Objective:	To compare the outcomes of dorsal column stimulation with Dorsal Root Ganglion stimulation in patients with Complex Regional Pain Syndrome that persist despite a course of conservative management including physical therapy and analgesic pharmacotherapy.
Study Design:	Prospective, randomized single center study. Patients will be randomized in a 1:1 ratio to Dorsal Column or Dorsal Root Ganglion stimulation after they have failed conservative treatment.
Patient Population:	Patients with Budapest criteria (research diagnostic definition) of Complex Regional Pain Syndrome occurring below the umbilicus who have not had an adequate response to conservative management including analgesic and physical therapies.
Enrollment Size and Number of Sites:	A total of 62 patients will be recruited from a single center
Primary Outcome:	50% change in index pain using a Numerical Rating Scale (NRS) at 6 months
Secondary Outcome:	30% change in function based on Oswestry Disability Index (ODI)
Additional Assessments:	
 • Change in Quality of Life as measured by EQ-5D • Change in Health Status measured by Short Form-36 (SF-36) • Pre and Post Procedure Pain medication usage • Global Improvement Impression of Change (PGIC) • Satisfaction with the pain relief, therapy in general, and likelihood of undergoing the therapy again for a similar outcome • Neurological assessment • Additional intervention(s)

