	
 • Anatomical spinal abnormality including severe central canal stenosis or bony foraminal impingement which could preclude device placement • Foreseen need for MRI to monitor or evaluate another chronic condition • Previous experience with an implanted or trial neuromodulation system (spinal cord stimulation, peripheral nerve stimulation) for the treatment of pain at the index location • Active local or systemic infection • Actively in litigation for pain symptoms • Currently on Workman’s Compensation • Women who are pregnant or intend to become pregnant during the study duration
Study Duration / Follow-up Period	Patients will be followed for an additional 6 months after device implant, with visits at 10 and 30 days, and 3 and 6 months post-procedure. Interim visits for device programming visits will be considered routine.
Baseline Visit	
 • Demographics: gender, age, height, weight • History • Characterization of the inciting event including duration of pain symptoms • Previous treatments including conservative management and physical therapy • Diagnosis and review of the inclusion and exclusion criteria • Neurological assessment • NRS for the index pain location • Pain medication usage (dosage and frequency)
Psychological Assessment	Psychological assessment will consider appropriateness for a neuromodulation system and for participation in a clinical device study.
Pre Trial Visit	
 • Neurological assessment • NRS for the index pain location • ODI • EQ-5D • SF-36 • Satisfaction with baseline management strategy • Pain medication usage (dosage and frequency)

	
 • Presurgical trial evaluation as stratified by the investigator including advanced imaging if necessary • Randomization
Trial Procedure	
 • Neurological assessment • NRS for the index pain location • Pain medication usage (dosage and frequency) • Trial of the study device
Trial Device Removal (7 days postop +/- 3 days)	
 • Wound check, trial device removal • NRS for index site pain • Neurological assessment • Additional intervention(s) • Complications / Adverse events

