Pre Implant Visit	
 • Neurological assessment • NRS for the index pain location • ODI • EQ-5D • SF-36 • Satisfaction with present management strategy • Pain medication usage (dosage and frequency) • Presurgical medical evaluation, history and physical examination, and additional special tests as stratified by the investigator including laboratory analysis, EKG, infectious screening, and/or advanced imaging
Implant Procedure	
 • Neurological assessment • NRS for the index pain location • Pain medication usage (dosage and frequency) • Implantation of the study device
Post-Operative Follow-up Visit (10 days postop +/- 3 days)	
 • Wound check, suture removal • NRS for index site pain • Neurological assessment • Additional intervention(s) • Complications / Adverse events
Follow-up Visit (30 days +/- 7 days)	
 • NRS for index site pain • Neurological assessment • ODI • EQ-5D

	
 • SF-36 • Pain medication usage (dosage and frequency) • PGIC • Additional intervention(s) • Complications / Adverse events • Radiograph to evaluate lead(s) position
Follow-up Visit (3 month +/- 14 days)	
 • NRS for index site pain • Neurological assessment • ODI • EQ-5D • SF-36 • Pain medication usage (dosage and frequency) • PGIC • Satisfaction questionnaire • Additional intervention(s) • Complications / Adverse events
Follow-up Visit (6 month +/- 14 days)	
 • NRS for index site pain • Neurological assessment • ODI • EQ-5D • SF-36 • Pain medication usage (dosage and frequency) • PGIC • Satisfaction questionnaire • Additional intervention(s) • Complications / Adverse events
Anticipated Unscheduled Visits	
 1. Radiograph to evaluate device positioning 2. Ad hoc programming of the study device
Site	Department of Evidence Based Pain Research Cleveland Clinic [name]

Table of Contents

1	INTRODUCTION	9
1.1	Background and Rationale.....	9
2	DEVICE DESCRIPTION.....	9
2.1	Device Indications for Use.....	9
3	STUDY PURPOSE AND OBJECTIVE.....	10
4	STUDY ENDPOINTS	10
4.1	Primary Endpoint.....	10
4.2	Additional Assessments.....	10
5	STUDY DESIGN.....	10
5.1	Overview.....	10
5.2	Sample Size and Number of Centers.....	11
5.3	Study Duration.....	11
6	STUDY PROCEDURES	12

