4.2 Additional Assessments

[figure not shown]
- Change in function based on Oswestry Disability Index (ODI)
- Global Improvement Impression of Change (PGIC)
- Change in Quality of Life as measured by EQ-5D
- Pre and Post Procedure Pain medication usage (dosage and frequency)
- Patient Satisfaction
- Procedure time
- Neurological assessment
- Additional intervention(s)
- Safety defined as adverse events related to the procedure or device

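### Supporting continuous outcomes: adjusting for the planned baseline scores would usually narrow the intervals at little cost, by an amount that depends on SDs and correlations the plan does not give

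*Combined protocol and SAP*

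**What the plan says.** Section 8.4 states that "DRG stimulation and SCS will be compared using a 2-sample t test (or Wilcoxon rank-sum test) for continuous outcomes". It continues: "Choice of parametric or alternative tests will be determined based on the data distributions for each measure". It gives no criterion for that choice. No section mentions a covariate, ANCOVA or any regression model. The primary endpoint is handled separately, as a responder proportion tested for noninferiority by the Blackwelder method.

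The synopsis words ODI, EQ-5D and SF-36 as change outcomes, for example "Change in Quality of Life as measured by EQ-5D". Section 4.2 does the same for ODI and EQ-5D. Neither section 4 nor 8.4 says from which value change is measured.

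The scores are scheduled as follows:

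- **Synopsis, Baseline Visit:** NRS is the only one of the four scores listed.
- **Synopsis, Pre Trial Visit:** NRS and "ODI • EQ-5D • SF-36 • Satisfaction with baseline management strategy". The list for this visit ends "including advanced imaging if necessary • Randomization".
- **Synopsis, Pre Implant Visit:** NRS and "ODI • EQ-5D • SF-36 • Satisfaction with present management strategy". This visit follows randomisation and the device trial.
- **Section 6.4:** all four scores are required at screening/baseline.
- **Table 1 (section 6.6):** NRS, ODI and EQ-5D are marked in the pre-op column. SF-36 is not.

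**The concern.** A 6-month score usually correlates with the same patient's starting score. An unadjusted comparison of 6-month scores ignores that correlation, and a comparison of changes fixes the slope on baseline at 1, whether or not 1 fits. ANCOVA estimates the slope. With few patients per arm, intervals for function and quality of life will be wide, and these baselines can narrow them without more patients, visits or instruments.

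The reference value matters as well. ODI, EQ-5D and SF-36 are taken twice before implant, the second time after the randomised device has been trialled. If change were measured from the Pre Implant value, part of the effect under comparison could be subtracted out. The plan does not say that this value will be used, but it does not exclude it.

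**Working it through.** **Inputs.** 62 patients, 31 per arm (section 5.2), and 15% attrition (section 8.3): 62 x 0.85 = 52.7, or about 26 per arm. Section 8.4 gives no level for the two-sided intervals, so 95% is assumed. The documents give no baseline-to-6-month correlation (rho) and no SDs. Rho is taken as 0.3 / 0.5 / 0.7, and the ratio k of 6-month SD to baseline SD as 0.75, 1 or 1.25.

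**The plan's own figure.** The only stated power is for the primary test. With 81% and 56%, a 5-point margin and 26 per arm, SE = sqrt((0.81 x 0.19 + 0.56 x 0.44)/26) = 0.124. At one-sided 0.05, power is Phi(0.30/0.124 - 1.645) = 78%, consistent with the stated figure of greater than 70%. Nothing below changes it. The plan gives no precision or power figure for supporting outcomes.

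**Interval width.** With baseline SD set to 1:

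- variance of change = 1 + k² - 2·rho·k
- variance of the 6-month score = k²
- residual variance under ANCOVA = k²(1 - rho²)

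Each large-sample width ratio is the square root of a variance ratio. The small-sample correction for N = 52 covers the estimated slope and the lost degree of freedom: sqrt(49/48) x t(0.975; 49)/t(0.975; 50) = 1.0104 x 2.0096/2.0086 = 1.011.

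Example with k = 1 and rho = 0.5: sqrt(0.75/1) = 0.866, and 0.866 x 1.011 = 0.875, so 12.5% narrower.

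| ANCOVA interval narrower than | rho 0.3 | rho 0.5 | rho 0.7 |
|---|---|---|---|
| t on change, k = 1 | 18.5% | 12.5% | 6.8% |
| t on change, k = 1.25 | 10.5% | 4.5% | -0.1% |
| t on change, k = 0.75 | 31.4% | 27.2% | 24.4% |
| t on 6-month score, any k | 3.6% | 12.5% | 27.8% |

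Simulation at k = 1 (40,000 trials per setting) gave ANCOVA-to-change width ratios of 0.815 / 0.875 / 0.932, in agreement, with coverage of 0.948 to 0.950.

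**Power.** Simulated with 26 per arm, two-sided 0.05, equal SDs and an assumed difference of 0.7 SD. The skewed setting is lognormal with sigma 0.6, also assumed; rho is then the latent correlation. Entries are for rho 0.3 / 0.5 / 0.7.

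| Analysis | Normal | Skewed |
|---|---|---|
| ANCOVA | 0.728 / 0.808 / 0.927 | 0.744 / 0.805 / 0.908 |
| t on change | 0.555 / 0.697 / 0.889 | 0.556 / 0.682 / 0.854 |
| Wilcoxon on change | 0.528 / 0.669 / 0.871 | 0.688 / 0.816 / 0.951 |
| Wilcoxon on 6-month score | not tabulated | 0.892 / 0.894 / 0.893 |
| Quade | 0.704 / 0.779 / 0.898 | 0.912 / 0.948 / 0.987 |

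In the skewed setting ANCOVA against Wilcoxon on change is +5.6 / -1.1 / -4.3 points. Against Wilcoxon on the 6-month score it is -14.8 / -8.9 / +1.5 points.

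**Type I error.** The plan's data-driven choice, modelled with an assumed Shapiro-Wilk rule at 0.05 on change scores, gave 0.049 to 0.056. ANCOVA and Quade gave 0.047 to 0.051.

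**The case against.** **The size of the gain is unknown.** A reader might take 7% to 18% as the expected gain. That range needs equal SDs, which the documents do not support or refute. A larger 6-month SD is plausible, because section 8.3 expects a mix of responders and non-responders in both arms. This objection stands. Over the SD ratios examined, the gain against change runs from about 0% to 31%.

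**The comparator is t or Wilcoxon, not t alone.** This also stands. Under the modelled test choice on change, the plan has power 0.674 / 0.788 / 0.939 in the skewed setting, so ANCOVA is better by 7.0 and 1.7 points and then worse by 3.1.

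**Quade could be the main analysis.** It loses 2 to 3 points to ANCOVA with normal data and gains 8 to 17 with skewed data. The reason to keep ANCOVA first is that it gives an adjusted difference and interval on the scale of the score. The power figures do justify running Quade for every measure.

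**The plan may already have a baseline.** Section 6.4 does designate one, and Table 1 has no Pre Implant column. A reader might infer that change will be taken from the Pre Implant value; no section says so. That the Pre Trial scores precede randomisation is itself only inferred from the order of the synopsis list, since section 6.3 says only that randomisation follows consent.

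**It is optional.** The planned tests are valid, and a reader who infers inflated error from the data-driven choice has no support for it in the check above. If the secondary ODI outcome is analysed as a 30% responder rate, it is untouched too.

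**Conclusion.** The point holds as a low-cost improvement for supporting continuous outcomes, not as an error in the plan. Against a t test on change, ANCOVA narrows the 95% interval by about 18% / 12% / 7% with equal SDs, with about 10% / 5% / 0% and 31% / 27% / 24% at SD ratios of 1.25 and 0.75. Against a t test on the 6-month score, the gain is about 4% / 13% / 28%. All of this assumes normal data, about 26 per arm and correlations of 0.3 / 0.5 / 0.7, none of which the documents can confirm beyond the numbers of patients. In these settings ANCOVA is essentially never wider than either t test. It is not uniformly more powerful than Wilcoxon when data are clearly skewed. The undefined reference value for change and the disagreement over baseline timing need settling whichever test is kept.

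**What to change.** Add to section 8.4:

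- Each continuous 6-month ODI, EQ-5D and SF-36 score (and NRS, if analysed as continuous) is compared by ANCOVA, with randomised group as factor and the pre-randomisation value of the same score as covariate, not the Pre Implant value. The adjusted difference is reported with its 95% CI. Randomised group needs stating because section 6.5 allows crossover after a failed trial.
- Quade rank ANCOVA is a pre-specified supporting analysis for every such measure, so that no switch depends on the observed distribution.
- The EQ-5D and SF-36 scores to be analysed are named. Any 30% ODI responder analysis remains a separate categorical comparison.

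Reconcile the synopsis (Pre Trial Visit), section 6.4 (screening/baseline) and Table 1 (no pre-op SF-36 mark) on when baseline ODI, EQ-5D and SF-36 are taken, and require that they are completed before the randomisation envelope is opened.

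**Cost.** A few sentences, one operational rule and one table row. Statistically, the cost is one degree of freedom (about 1% wider than a t test on the 6-month score at zero correlation) and a gain near zero if the 6-month SD clearly exceeds baseline and the correlation is high. In the assumed skewed setting, power falls by about 1 to 4 points against Wilcoxon on change at correlations 0.5 to 0.7, and by about 9 to 15 points against Wilcoxon on the 6-month score at 0.5 to 0.3. The Quade analysis is there to cover that case.
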